6.10 Adverse Events Assessments

6.10.1 Definitions of Adverse Events and Serious Adverse Events

6.10.1.1 Adverse Event

An AE is any noxious, pathologic, or unintended change in anatomical, physiologic, or metabolic function as indicated by physical signs, symptoms, or laboratory changes occurring in any phase of a clinical study, whether or not considered investigational product-related. This includes an exacerbation of a pre-existing condition.

Adverse events include:

- Worsening (change in nature, severity, or frequency) of conditions present at the onset of the study
- Intercurrent illnesses
- Drug interactions
- Events related to or possibly related to concomitant medications
- Abnormal laboratory values (This includes significant shifts from baseline within the range of normal that the Investigator considers to be clinically important.)
- Clinically significant abnormalities in physical examination, vital signs, and weight

Throughout the study, the investigator must record all AEs on the AE eCRF, regardless of the severity or relationship to investigational product. The investigator should treat patients with

AEs appropriately and observe them at suitable intervals until the events stabilize or resolve. Adverse events may be discovered through observation or examination of the patient, questioning of the patient, complaint by the patient, or abnormal clinical laboratory values.

In addition, AEs may also include laboratory values that become significantly out of range as determined by the investigator or in the opinion of the investigator. In the event of an out-of-range value, the laboratory test should be repeated until it returns to normal or can be explained and the patient's safety is not at risk.

Additional illnesses present at the time when informed consent is obtained are regarded as concomitant illnesses and will be documented on the appropriate pages of the eCRF. Illnesses first occurring or detected during the study, and worsening of a concomitant illness during the study, are to be regarded as AEs and must be documented as such in the eCRF.

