5 STATISTICAL ANALYSIS

5.1 General Methodology

All analysis will be performed by the Biometrics Department, Shire HGT using SAS[®] Software version 9.3 or higher (SAS institute, Cary, NC, USA). All study data will be presented in by-patient data listings.

No formal statistical tests will be conducted. Tabular summaries of patient baseline demographic and clinical characteristics, patient disposition, medical history, vital signs, AEs, anti-agalsidase alfa antibody, and infusion information will be produced for the safety population. The safety population includes all patients who receive at least one full or partial infusion of Replagal. Continuous data collected prior to receiving study drug and at subsequent visits will be summarized using descriptive statistics (n, mean, median, minimum, maximum, and standard deviation). Categorical data will be summarized as frequencies and percentages. All data summaries will be presented for each cohort and overall, as appropriate, unless otherwise indicated

Cohort:

Cohort is defined as:

- Cohort 1: Patients from CFDI and receiving Replagal on EOW regimen
- Cohort 2: Patients who participated in REP001a and receiving Replagal on weekly regimen

Data Derivations:

The following key derived and computed variables have been initially identified. It is expected that additional variables may be required. The SAP will not be amended for additional variables. All derived and computed variables, including additional variables later identified, will be documented in the “Define Document,” and also in the SAS analysis dataset creation programs. The following are anticipated data derivations:

- *Screening period:* Within 6 months prior to first dose
- *Pre-treatment period:* Prior to first study drug infusion
- *Day 1:* Day of first study drug infusion
- *Date of Enrollment (entry):* Date informed consent is signed
- *Baseline:* Last valid non-missing assessment made prior to the first study drug infusion.
- *Change from Baseline:* Post-baseline value – Baseline Value

- *% Change from Baseline:* $\{(Change\ from\ Baseline / Baseline) * 100\}$
- *Change from Pre-infusion:* Value immediately after infusion – value immediately before infusion.
- *% Change from Pre-infusion:* $\{(Change\ from\ pre-infusion / pre-infusion) * 100\}$
- *Age:* integer of $\{(date\ of\ informed\ consent - date\ of\ birth) / 365.25\}$
- *Duration of study drug exposure:* (Date of last infusion – date of first infusion)+1

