5.7.2 Clinical Laboratory Evaluations

Blood will be collected within 6 months prior to the patient receiving the first dose of Replagal and at the biannual/annual safety visits for the following assessments: creatinine, glucose, blood urea nitrogen (BUN), potassium, sodium, chloride, bicarbonate, and fasting lipids profile (total cholesterol, HDL cholesterol, LDL cholesterol, and triglycerides).

The observed values and change from baseline will be summarized by biannual visit for laboratory data using descriptive statistics. Shift tables will also be presented comparing the baseline values to those at each biannual visit. Shifts over time will be presented by low, normal, and high. The numbers (and percentages) of patients within each category will be tabulated. Lab assessments will be summarized by cohort, previous ERT status and overall based on the safety population.

Any patient, who had a clinically significant abnormal value, as determined by the investigator, will be listed.

All laboratory data from both scheduled and unscheduled (i.e., unexpected) visits will be presented in the data listings for the safety population. However, for the summary tables only laboratory data associated with scheduled visits will be summarized.

If there are repeated or retest laboratory measurements associated with a given study visit then, in general, the second set of measurements with respect to date/time order, will be used for the statistical analysis unless the values are invalid or missing. In this instance a value from the first set of measurements will be used provided it is valid and non-missing.

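### The SAP analyses the second laboratory value at a visit, but the protocol asks for repeats only of out-of-range values, so shift tables under-count abnormalities whose retest is filed to the visit

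*SAP*

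**What the plan says.** Four rules act together.

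- **Which value is analysed.** SAP 5.7.2, on repeat or retest measurements belonging to a study visit: "in general, the second set of measurements with respect to date/time order, will be used for the statistical analysis". The exception is a second set that is invalid or missing: "In this instance a value from the first set of measurements will be used provided it is valid and non-missing".
- **When a test is repeated.** Protocol 6.10.1.1: "In the event of an out-of-range value, the laboratory test should be repeated until it returns to normal or can be explained", provided also that the patient is not at risk. This is the only laboratory-repeat instruction in either document.
- **Which tables use the value.** SAP 5.7.2: "Shift tables will also be presented comparing the baseline values to those at each biannual visit", and "Shifts over time will be presented by low, normal, and high". The same section limits the input: "for the summary tables only laboratory data associated with scheduled visits will be summarized".
- **Baseline.** SAP 5.1 defines it as "Last valid non-missing assessment made prior to the first study drug infusion", so a pre-dose retest can become the baseline.

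Everything is still listed: "All laboratory data from both scheduled and unscheduled (i.e., unexpected) visits will be presented in the data listings for the safety population". Protocol 7.5 adds that abnormal values are flagged in the listings, and SAP 5.7.2 lists patients with values that the investigator calls clinically significant. No worst-value table is planned. The only sensitivity analysis (SAP 7.7) concerns outliers.

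**The concern.** Whether a second value exists depends on the first value. Abnormal results get a second look and normal results do not, and the SAP then keeps the second look. Transient and borderline abnormalities drop out of the tables, and nothing prescribed brings any in.

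The study's only objective is safety, no formal tests are planned, and SAP 1.2 says the analyses go into regulatory submissions. The descriptive tables are therefore the result. Blood tests are one of its objective safety measures. Abnormalities that the investigator did not record as adverse events would be under-counted on treatment, which makes the absolute counts look more favourable to the product.

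**Working it through.** The plan gives no figure for this point, so there is none to reproduce. The direction comes from the text. The size needs assumptions.

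**Direction.** A visit result is tabulated as abnormal if the first value is abnormal and either no retest is filed to that visit or the retest is also abnormal. A first value in range has no prescribed retest and stays normal. Hence

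reported rate = p − f × (p − b),

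where p is the out-of-range rate on first values, b is the probability that first value and retest are both out of range, and f is the share of out-of-range results that are retested and filed to the scheduled visit. Because b cannot exceed p, the reported rate cannot exceed p.

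**Assumptions (none is in the documents).** Values are normally distributed, with equal correlation ρ among baseline, visit and retest values. The limits are ±1.96 SD, so p = 5.0%. ρ is 0.7 to 0.9 and f is 0 to 1. Under this model b = 1.65%, 2.19% and 2.96% at ρ = 0.7, 0.8 and 0.9.

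**Reported out-of-range rate when first values give 5.0%**

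| f | ρ = 0.7 | ρ = 0.8 | ρ = 0.9 |
|---|---|---|---|
| 1 | 1.65% | 2.19% | 2.96% |
| 0.5 | 3.33% | 3.60% | 3.98% |
| 0.25 | 4.16% | 4.30% | 4.49% |
| 0 | 5.0% | 5.0% | 5.0% |

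Example: f = 0.5, ρ = 0.7 gives 5.0 − 0.5 × (5.0 − 1.65) = 3.33%. For the minimum of 60 patients, 60 × 5.0% = 3.0 abnormal results per analyte and visit. This becomes 60 × 1.65% = 1.0 to 60 × 2.96% = 1.8 with f = 1, and 2.5 to 2.7 with f = 0.25.

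**A higher abnormal rate.** If 10% of first values lie above one limit and f = 1, the reported rate is 4.7% at ρ = 0.7 and 6.9% at ρ = 0.9.

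**Whole-panel redraws.** SAP 5.7.2 names 11 analytes (seven chemistries and four lipids). If any out-of-range analyte triggers a redraw of all 11, and the analytes are independent, an analyte is redrawn for another's sake with probability 1 − 0.95^10 = 0.401. In that case its second value is an unselected draw. The reported rate is 0.401 × 5.0% + 0.599 × 1.65% = 3.0% at ρ = 0.7, and 0.401 × 5.0% + 0.599 × 2.96% = 3.8% at ρ = 0.9. The bias is diluted but not removed.

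**A true upward shift of 0.5 SD** (simulated, same rule at baseline and visit)

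| Quantity | ρ = 0.7 | ρ = 0.8 | ρ = 0.9 |
|---|---|---|---|
| Normal-to-high, first values | 5.74% | 5.39% | 4.98% |
| Normal-to-high, SAP rule, f = 1 | 2.56% | 2.93% | 3.39% |
| Normal-to-high, SAP rule, f = 0.5 | 4.23% | 4.22% | 4.22% |

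With f = 1 the mean change falls only from 0.50 SD to 0.46 SD (ρ = 0.7) or 0.49 SD (ρ = 0.9), and with no true shift it is unaffected. The tables of means would not reveal the loss.

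**Why baseline must change with the visit value** (no drug effect, f = 1; normal-to-abnormal against abnormal-to-normal)

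| Rule | ρ = 0.7 | ρ = 0.9 |
|---|---|---|
| SAP rule at both times | 1.1% each way | 1.1% each way |
| First value at the visit only | 4.1% vs 0.8% | 2.7% vs 0.7% |
| First value at both times | 3.3% each way | 2.0% each way |

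Correcting the visit alone would produce apparent worsening where there is none.

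**The case against.** **The bias depends on filing.** A retest on a later day may be recorded as an unscheduled visit. It then stays out of the tables, the first value remains, and nothing is lost. The documents do not say which happens. This stands, and it is why the range runs down to no effect. But SAP 5.7.2 writes a rule for retests belonging to a visit, so some are expected. If sites file differently, the tables mix two rules.

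**The retest instruction may be narrower.** It sits within the adverse event definition, directly after values that the investigator judges significantly out of range, and repeats may also stop once a value is explained. Some abnormal results, such as raised creatinine in patients who qualified on renal criteria, may never be retested. That lowers f but does not change the direction.

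**The rule counts confirmed abnormalities, which is a legitimate target.** At a true 0.5 SD shift with ρ = 0.7 and f = 1, normal-to-high shifts are 2.56% against 0.54% with no effect, a ratio of 4.7; first values give a ratio of 3.4. At ρ = 0.9 the ratios are 6.3 and 4.9. So the relative contrast with chance shifts rises, and with no drug effect the rule creates no net shift. Both points are correct. However, the absolute number of on-treatment abnormalities still falls, and that is what a descriptive safety table reports. The SAP does not define its target as confirmed abnormality, and genuine transient abnormalities go out with the chance ones.

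**Other outputs keep the values.** Flagged listings, the listing of clinically significant values and the adverse event tables preserve much of the information. They limit the harm without correcting the tabulated counts, and two of the three depend on investigator judgement.

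**Conclusion.** The concern holds. For retests filed to a scheduled visit, the two rules together can only remove abnormal results from the shift tables under the retesting that the protocol prescribes. Within the assumed model, a 5.0% out-of-range rate is reported as 1.7% to 3.0% at the upper bound of the loss, as 4.2% to 4.5% if a quarter of abnormal results are affected, and correctly if none are. Retest rate, filing practice, correlation and the 5.0% rate are all assumptions.

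This is a reporting bias in secondary safety tables. No formal test depends on it, and the underlying values remain in the listings. It should be fixed because the direction is known, the study reports only safety, and the data needed are already collected.

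**What to change.** 1. **SAP 5.7.2.** Use the first valid scheduled measurement for by-visit summaries and shift tables. Let a retest replace it only when the first sample is documented as invalid. Delete the words that leave the choice open (the rule now applies only in general). This also settles third and later repeats, on which the SAP is silent although the protocol allows them.
2. **SAP 5.1, for laboratory data.** Define baseline in the same way: the first valid measurement of the last scheduled collection before the first infusion. Items 1 and 2 must be made together.
3. **SAP 5.7.2, one added table.** Present a shift from baseline to the worst post-baseline value, using all scheduled, unscheduled and retest results. On-treatment abnormalities are then counted however the retest was filed.

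The cost is wording in two sections and one extra table, with no new samples or visits. Reported abnormality rates will rise slightly and will include some transient or chance abnormalities; a footnote should say so.

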5.7.3 Vital Signs

Vital signs, including blood pressure, pulse, respiratory rate, and temperature, will be measured immediately prior to each infusion and immediately following each infusion (\pm 10 minutes). Vital signs will be summarized by cohort, previous ERT status and overall based on the safety population.

The observed values immediately prior to first infusion at baseline and immediately after infusion at the end of study (EOS) visit, and changes from these values baseline to EOS will be summarized using descriptive statistics for temperature, pulse, respiration rate, systolic and diastolic blood pressure, and weight. Additionally, height at baseline will also be summarized.

Within each visit the observed values immediately prior to infusion and after infusion will be summarized using descriptive statistics. Changes from immediately prior to infusion to and after infusion will also be summarized.

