6.5 Physical Examination

Complete physical examinations will occur prior to the first dose of Replagal administration and during the biannual or annual safety visits, as applicable. The physical examinations will include assessments of:

- Head, neck, and thyroid
- Eyes, ears, nose, and throat
- Chest and lungs
- Heart
- Lymph nodes
- Abdomen
- Anorectal
- Genitourinary
- Skin
- Musculoskeletal
- Endocrine
- Neurological
- Height (measured at baseline for all patients, and for patients <18 years at baseline, height will also be measured at biannual or annual safety visits until they are ≥ 18 years of age)
- Weight (within 1 month prior to the first Replagal infusion)
- Other

Clinically significant findings from the physical examinations are to be reported as AEs.

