3.6 Determination of Sample Size

Health Canada requested that a minimum number of patients be specified in order to obtain meaningful safety data from this safety clinical trial. With a minimum of 60 subjects, there will be at least a 95% chance of observing at least one adverse event (AE) of a given type, if the event has a frequency of 5%.

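### Change-from-baseline tables for laboratory values, vital signs and weight pool growing children with adults, and height measured after baseline in children has no planned summary

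*SAP*

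**What the plan says.** The protocol sets no age limit in its criteria (section 4) and provides for parental consent and assent (6.16). SAP 5.6.3 defines an age group of <18 and ≥18 years.

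On vital signs, SAP 5.7.3 states: "Vital signs will be summarized by cohort, previous ERT status and overall based on the safety population". The changes from baseline to the end-of-study (EOS) visit "will be summarized using descriptive statistics for temperature, pulse, respiration rate, systolic and diastolic blood pressure, and weight". On laboratory data, where change from baseline is summarised by visit and creatinine is included, SAP 5.7.2 states: "Lab assessments will be summarized by cohort, previous ERT status and overall based on the safety population". Neither section names age group or any age-standardised value.

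On height, protocol 6.5 measures everyone at baseline. For patients under 18 at baseline, "height will also be measured at biannual or annual safety visits until they are" 18 or older. The SAP schedule repeats this. The only height analysis in SAP 5.7.3 is: "Additionally, height at baseline will also be summarized".

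Age group is a named breakdown elsewhere: demographics (SAP 5.5.1), and adverse events, infusion-related reactions, serious adverse events and discontinuations (5.7.1).

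**The concern.** Weight, creatinine, pulse and blood pressure all change as a child grows, and follow-up here is open-ended. A table that averages change from baseline over children and adults reports a mixture of maturation in the children and whatever happened to the adults. A reader of the overall row cannot tell a small drift in adults from a few children growing up, and slow growth in the children would be diluted by the adults. The age split that would separate the two is already defined in the SAP and used for other tables. Safety is the only objective, so these tables are part of the main result.

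**Working it through.** **1. The plan's own figure.** SAP 3.6 claims at least a 95% chance of seeing one or more events of a type with 5% frequency in 60 patients. 1 − 0.95^60 = 0.954, so it reproduces and is not in dispute. There is no other design figure to check: "No formal statistical tests will be conducted".

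**2. Does the general subgroup clause reach these tables?**

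| SAP section | What it commits to |
|---|---|
| 5.6.3 | Subgroup analyses by sex, age group, previous ERT, ADA and NAb status, where applicable |
| 7.6 | Everything overall and by cohort; only selected analyses by previous ERT and/or age group, as already specified |
| 5.5.1, 5.7.1 | Age group named |
| 5.7.2, 5.7.3 | Cohort, previous ERT and overall; age group not named |

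Read together, 7.6 points back to the individual sections, and 5.7.2 and 5.7.3 specify previous ERT status but not age. Table shells built from those sections would have no age rows.

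**3. Size for weight.** The documents give no number of children, growth rate or SD, so all of these are assumptions: fraction of children c = 5–15%, gain g = 3–5 kg per year, follow-up T = 3–5 years, adults unchanged on average. Multi-year follow-up is plausible from the documents: the original protocol is dated September 2010 and Amendment 5 March 2015, treatment is open-ended, and patients in the interim analysis who had not withdrawn had 24 months.

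Shift in pooled mean = c × g × T; children's own mean = g × T.

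| c | g | T | Pooled shift (kg) | Children's mean (kg) |
|---|---|---|---|---|
| 0.05 | 3 | 3 | 0.45 | 9 |
| 0.10 | 5 | 5 | 2.50 | 25 |
| 0.15 | 5 | 5 | 3.75 | 25 |

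Outside that range, at c = 0.02, g = 3 and T = 2, the shift is 0.12 kg.

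**4. Masking.** If children gained only half the expected weight, their own mean would fall short by g × T / 2 = 4.5 to 12.5 kg. The pooled mean would move by only c × g × T / 2 = 0.225 to 1.875 kg.

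**5. Spread.** With an assumed within-group SD of 4 kg, pooled SD = √(16 + c(1 − c)(gT)²). This gives √(16 + 0.0475 × 81) = 4.5 kg at the low end and √(16 + 0.1275 × 625) = 9.8 kg at the high end.

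**6. Creatinine.** With an assumed rise in children of 2–4 µmol/L per year and the same c and T, the pooled shift is 0.05 × 2 × 3 = 0.3 to 0.15 × 4 × 5 = 3.0 µmol/L.

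**7. Size of a paediatric row.** With 60 patients, 5–15% is 3 to 9 children; with 200 it is 10 to 30.

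**8. Which tables are exposed.** Only baseline-to-later changes are. The change from immediately before to immediately after an infusion compares two readings from the same visit, and growth cannot move it.

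**The case against.** The strongest reply is that SAP 5.6.3 already promises age-group analyses, so the split is not absent. That is fair as far as it goes: the defect is a commitment of unclear reach, and 7.6 makes the narrow reading the natural one.

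A reader might infer that paediatric growth safety is lost, or that height is never looked at. The documents do not support that. SAP 5.1 puts all study data into by-patient listings. Protocol 6.10.1.1 counts clinically significant abnormalities in weight and vital signs as adverse events, and the SAP tabulates adverse events by age group. Growth is not a stated objective or endpoint, and no passage says that serial height is collected for growth safety. What stands is narrower: no post-baseline height summary is planned. Whether serial height reaches a listing is also unconfirmed, because SAP 5.7.4 says physical examination data are not in the CRF and protocol 6.5 places height and weight within that examination.

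A reader might also infer that the vital-sign analysis as a whole is contaminated. It is not: SAP 4.4 defines the vital-sign assessment as the change across each infusion.

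Other points soften the effect. Summaries include the median, minimum, maximum and SD. With 10% children all above the median and an adult SD of 4 kg, the median moves about 0.56 kg (4 × 0.14, the normal quantile at 0.5/0.9), against 2.5 kg for the mean at 5 kg per year over 5 years. Low/normal/high shift tables for creatinine would be largely protected if reference ranges are age-specific, which the SAP does not state. And in a descriptive single-arm study no pooled mean identifies a drug effect. These points reduce the harm, but none gives the reader a separate adult row.

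**Conclusion.** The concern holds in limited form. As written, SAP 5.7.2 and 5.7.3 average baseline-to-later changes over children and adults, and height measured after baseline only in patients <18 has no planned summary. The weight shift from growth alone is 0.45–3.75 kg under the stated assumptions and could be close to zero if very few children enrolled. Everything about its size rests on a paediatric fraction and growth rate that the documents do not give. It would go too far to say that growth will be reported as a drug effect: the plan makes no such attribution and tests nothing. This is an inexpensive improvement to how the tables can be read, not a flaw that undermines the study.

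**What to change.** - In SAP 5.7.2 and 5.7.3, name age group (<18, ≥18 at baseline) as a breakdown for the change-from-baseline tables, and read these changes from the age rows rather than the overall row.
- For patients <18 at baseline, summarise height and weight by safety visit as age- and sex-standardised scores alongside raw values. Raw kilograms and centimetres alone would still mix younger children with adolescents and could not separate normal from slow growth. If numbers are too small, state that listings only will be given.
- Confirm that serial height is captured in the CRF, given SAP 5.7.4.
- Reconcile SAP 5.7.3 with the schedules in both documents. It analyses weight and post-infusion vital signs at the EOS visit, where the schedules mark only adverse event assessment.

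The cost is SAP wording and table shells, provided that serial height is in the database. The downside is a small paediatric row, perhaps 3 to 9 patients if only 60 enrol.
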